**Vraag 7b. Welke bloedverdunners heeft u in de afgelopen 3 maanden gebruikt?**

Met bloedverdunners bedoelen we alle medicijnen die bij vraag 7a na het sterretje (\*) worden genoemd. U ziet eerst twee voorbeelden.

Let op: pak de verpakking erbij! Daarop staat hoeveel u per keer moest nemen. En hoe vaak u dat moest doen. Heeft u meer of minder gebruikt? Vul dan in hoeveel u ook echt gebruikt heeft. Hoe heet het medicijn?	Hoeveel heeft u per keer genomen? Kijk op de verpakking	Hoe vaak op een dag heeft u dit gedaan? Kijk op de verpakking	Op hoeveel dagen in de afgelopen 3 maanden heeft u het medicijn gebruikt?
Voorbeeld 1 Carbasalaatcalcium	Voorbeeld 100 mg	Voorbeeld 1 keer	Voorbeeld 14 dagen
Voorbeeld 2 Clopidogrel	Voorbeeld 75 mg	Voorbeeld 1 keer	Voorbeeld 90 dagen

**Vraag 8a. Bent u in de afgelopen 3 maanden in het ziekenhuis geweest voor een bezoek aan een arts of spoedeisende hulp? Opnames in het ziekenhuis (dus met overnachting) tellen hier niet mee, het gaat alleen om bezoeken overdag**

- Nee  
 Ja

Heeft u “Ja” geantwoord? Beantwoord dan vraag 8b.  
Ga anders verder met vraag 9.

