#### **10.5 Other study parameters**

The cost-effectiveness will be calculated by comparing the costs for patients with good functional outcome, costs per QALY and costs for the intervention and hospital admissions. Quality of life will be assessed with the EuroQol-5D-5L. Costs for potential productivity loss will be assessed with a set of questions from the iMTA Productivity Cost Care (iPCQ) and costs for any other relevant healthcare resource use will be measured by a set of questions from the iMTA Medical Consumption Questionnaire (iMCQ).

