**Vraag 1b. Hoeveel afspraken had u in de afgelopen 3 maanden met uw huisarts?**

- ..... afspraken met de huisarts

**Vraag 2. Hoeveel afspraken had u in de afgelopen 3 maanden met een fysiotherapeut? Of met een caesartherapeut, therapeut mensendieck of een manueel therapeut?** Tel alle afspraken met deze therapeuten bij elkaar op.

- Geen enkele afspraak  
 ..... afspraken

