### Question 1b. How many appointments did you have with your general practitioner in the past 3 months?

- ..... appointments with a doctor  
 ..... appointments with a nurse practitioner

**Question 2. How many appointments did you have with a physiotherapist in the past 3 months? Or with a Caesar therapist, therapist Mensendieck or a manual therapist?** Add up all appointments with these therapists.

- No appointment
- ..... appointments

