**Question 7a. Did you take any blood thinners\* in the past 3 months?**

No

Yes

\* carbasalatecalcium (ascal, acetylsalicylic acid), clopidogrel (plavix, grepid, iscover), prasugrel (efient) , ticagrelor (brilique), dipyidamole (persantin), acenocoumarol (sintrom), fenprocoumon (marcoumar), dabigatran (pradaxa), rivaroxaban (xarelto), apixaban; (eliquis), edoxaban (lixiana)

Have you ticked "Yes"? Then fill in question 7b listing which medications you used and how much.

Otherwise, continue with question 8.

**Question 7b. What blood thinners did you take in the past 3 months?** By blood thinners we mean all drugs listed in Question 7a after the asterisk (\*). There are twoexamples below.

**Pay attention:** look at the package! It shows how much you had to take at each time. And how often you had to do so per day. ***Have you used more or less? Then enter how much you have actually used.***

What is the name of the medicine?	How much did you take at each time? Look at the packaging	How many times did you take this per day? Look at the packaging	On how many days in the past 3 months have you used the medication?
example 1 Carbasalate calcium	example 100 mg	example 1 time	example 14 days
example 2 clopidogrel	example 75 mg	example 1 time	example 90 days
.....	.....	.....	.....
.....	.....	.....	.....
.....	.....	.....	.....
.....	.....	.....	.....
.....	.....	.....	.....
.....	.....	.....	.....
.....	.....	.....	.....
.....	.....	.....	.....

**Question 8a. Did you have an appointment at the outpatient clinic of the hospital in the past 3 months?** It is about appointments for yourself with a doctor. For example with the cardiologist, rheumatologist or neurologist. Hospital admissions (i.e. with an overnight stay) do not count here, it is only regarding daytime visits.

- No
- Yes

Have you ticked "Yes"? Then fill in question 8b the types of doctors you have visited. And how often. There is an example in the first row. Otherwise, continue with question 9.

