**Question 1a. Avez-vous consulté un médecin généraliste au cours des trois derniers mois ?**

- Non  
 Oui

Vous avez coché « Oui » ? Vous devez alors répondre à la question 1b.  
Si vous avez coché « Non », vous pouvez passer à la question 2.

**Question 1b. Combien de consultations avez-vous effectuées avec votre médecin traitant au cours des trois derniers mois ?**

- ..... consultations avec le médecin traitant

**Question 2. Combien de consultations avez-vous effectuées avec un physiothérapeute au cours des trois derniers mois ? Ou avec un thérapeute César, un thérapeute Mensendieck ou un thérapeute manuel ?** Ajoutez toutes les consultations avec de tels thérapeutes.

- Aucune consultation  
 ..... consultations

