**Question 7a. Avez-vous pris des médicaments anticoagulants\* au cours des trois derniers mois ?**

Non

Oui

\* carbasalaatcalcium (ascal, acetylsalicylzuur), clopidogrel (plavix, grepid, iscover), prasugrel (efient) , ticagrelor (brilique), dipyidamol (persantin), acenocoumarol (sintrom), fenprocoumon (marcoumar), dabigatran (pradaxa), rivaroxaban (xarelto), apixaban; (eliquis), edoxaban (lixiana)

Vous avez coché « Oui » ? Vous devez alors répondre à la question 7b et dresser une liste des médicaments que vous avez utilisés avec la quantité administrée. Si vous avez coché « Non », vous pouvez passer à la question 8.

**Question 7b. Quels médicaments anticoagulants avez-vous pris au cours des trois derniers mois ?** Les médicaments anticoagulants comprennent tous les types de médicaments énumérés à la question 7a après l'astérisque (\*). Vous pouvez retrouver deux exemples ci-dessous.

**Attention** : lisez attentivement la posologie ! Elle indique combien vous avez dû en prendre à chaque fois. Et la fréquence avec laquelle vous avez dû le faire chaque jour. **Vous avez utilisé plus ou moins ? Veuillez alors indiquer la quantité réellement utilisée.**

Quel est le nom des médicaments ?	Combien en avez-vous pris à chaque fois ? Regardez la posologie	Combien de fois en avez-vous pris par jour ? Regardez la posologie	Combien de jours au cours des trois derniers mois avez-vous utilisé le médicament ?
exemple 1 carbasalaatcalcium	exemple 100 mg	exemple 1 fois	exemple 14 jours

exemple 2	exemple	exemple	exemple
Clopidogrel	75 mg	1 fois	90 jours
.....	.....	.....	.....
.....	.....	.....	.....
.....	.....	.....	.....
.....	.....	.....	.....
.....	.....	.....	.....
.....	.....	.....	.....
.....	.....	.....	.....
.....	.....	.....	.....

**Question 8a. Avez-vous eu une consultation à la polyclinique de l'hôpital au cours des trois derniers mois ?** Il s'agit de consultations pour vous-même avec un médecin. Par exemple avec un cardiologue, un rhumatologue ou un neurologue.

Autrement dit, sans passer de nuit à l'hôpital

- Non  
 Oui

Vous avez coché « Oui » ? Vous devez alors répondre à la question 8b sur les types de médecins que vous avez consultés. Et à propos de la fréquence. Vous pouvez retrouver un exemple à la première ligne.

Si vous avez coché « Non », vous pouvez passer à la question 9.

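### The iMCQ names emergency-department visits only in Dutch and nurse-practitioner contacts only in English, so recorded resource use is not comparable across languages

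*Protocol*

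**What the plan says.** Section 10.5 of the Protocol relies on the iMCQ for the cost-effectiveness analysis: "costs for any other relevant healthcare resource use will be measured by a set of questions from the iMTA Medical Consumption Questionnaire (iMCQ"). The questionnaire is reproduced in Dutch (17.7), English (17.8) and French (17.9).

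Question 8a, on hospital visits without an overnight stay:
- Dutch: "Bent u in de afgelopen 3 maanden in het ziekenhuis geweest voor een bezoek aan een arts of spoedeisende hulp"
- English: "Did you have an appointment at the outpatient clinic of the hospital in the past 3 months", with the clarification "It is about appointments for yourself with a doctor"
- French: "Avez-vous eu une consultation à la polyclinique de l'hôpital au cours des trois derniers mois"

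Question 1b, on general-practice contacts:
- Dutch: one line, "afspraken met de huisarts"
- French: one line, "consultations avec le médecin traitant"
- English: a line for the doctor and a second line, "appointments with a nurse practitioner"

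**The concern.** A cost analysis that combines answers from three language versions needs each version to count the same contacts. Here the emergency department is named in one version and not in the other two, and a separate nurse-practitioner count exists in one version and not in the other two. The same care can then produce different recorded use, and so different cost, depending only on the form a patient received.

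Cost-effectiveness is the tertiary objective (section 2), and an expected cost advantage is part of the argument for the non-inferiority design (section 4.5). The Protocol also expects the arms to differ in events that could lead to an unplanned hospital contact: early recurrent ischaemia under deferred treatment (Summary, 7.4, 13.1) and bleeding under longer dual antiplatelet therapy after immediate stenting (11.4). Information that a form never asks for cannot be restored by an analysis plan.

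**Working it through.** The Protocol gives no figure to reproduce, so the check is an item-by-item comparison of the three current texts.

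**Emergency visits**
1. Dutch 8a covers a visit to a doctor in hospital or to the emergency department, and excludes overnight stays.
2. English and French 8a cover an appointment or consultation at the hospital outpatient clinic, also excluding overnight stays. Neither names the emergency department.
3. The remaining English and French items are: general practitioner and therapists (1 to 5), home care (6), blood thinners (7), overnight hospital stay (9) and other institutions (10). None asks about an emergency visit without admission.
4. In all three versions, No at 8a sends the respondent past 8b to question 9.
5. So a patient seen in the emergency department, sent home, and with no other hospital contact answers Yes on the Dutch form. On the English or French form the proper answer is No, and the visit leaves no trace.
6. A respondent on those forms who also had an outpatient appointment does reach 8b. There the free-text rows for type of doctor may pick up an emergency doctor. The loss is therefore partial.

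**Nurse-practitioner contacts**

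The English form has a separate count. The Dutch and French forms have no place for it, so such contacts are either omitted or absorbed into the doctor count.

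**Bound on the size**

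Let *s* be the share of participants on English or French forms. If emergency visits without admission are equally frequent across languages, the fraction lost trial-wide is at most *s*, reached only if every such visit on those forms goes unrecorded.

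The Protocol does not state *s*. As an illustration of the ceiling for French forms alone:
- Section 4.1 gives about 2000 yearly thrombectomies in the Netherlands and 1000 in Belgium. Assume that enrolment follows this split: 1000/3000 = 33.3% Belgian.
- Assume that 30%, 40% or 50% of Belgian participants use the French form (not in the Protocol).
- 0.333 × 0.30 = 10.0%; 0.333 × 0.40 = 13.3%; 0.333 × 0.50 = 16.7%.

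English forms would add to this by an unknown amount. The figures are upper limits on one cost component. They do not estimate the loss, and they say nothing about total cost, because no visit frequencies or unit costs are given.

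**Direction of the between-arm effect**

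Write the arm difference in emergency-visit cost (immediate stenting minus deferred) as *b* − *r*, where *b* is the excess from bleeding and *r* the reduction from fewer recurrent ischaemic events. Incomplete recording removes part of *b* and part of *r*. The sign of *b* − *r* is unknown, so the direction in which the total cost difference moves is unknown too.

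**The case against.** The strongest reply is that little is lost and that part of it can be recovered.

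- **Question 8b is open.** Anyone with an outpatient appointment reaches it and may list an emergency doctor. This stands: it is wrong to say that all emergency visits on English and French forms are recorded as zero.
- **The Dutch form does not isolate emergency visits either.** Dutch 8b asks for type of doctor and number of visits and has no emergency row. This stands, and it means that a rule treating emergency visits as a separately recorded component would not work even for Dutch forms.
- **Other sources exist.** Section 20 plans linkage of Belgian participants to administrative cost data for the KCE analysis, which may recover visits in the group most likely to use French forms. It depends on a separate authorisation, serves KCE's own analysis and leaves the questionnaires unequal. Recurrent events, bleeding and adverse events are also recorded (8.1.2, 8.1.3, 9.2.1), but as clinical events rather than as counts of care used.
- **How the versions are combined is analysis-plan detail.** Section 10.5 does not describe the pooling, and that is not held against it here. No later plan can supply answers to a question that was not asked.

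Two stronger readings are tempting. A reader might infer that one arm is favoured. The documents do not support this: randomization is stratified by centre (8.2), so language should be roughly balanced between arms, and the expected events pull in opposite directions. A reader might also take the 10% to 17% range as the size of the undercount. It is a ceiling that rests on an assumed French share and on national treatment volumes, not on planned accrual.

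**Conclusion.** The point holds as a mismatch of content between language versions. Emergency visits without an overnight stay are asked about in Dutch and not in English or French, and nurse-practitioner contacts are counted separately only in English. Resource use measured for section 10.5 is therefore not comparable across languages, and some emergency visits on English and French forms will be lost.

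The size cannot be computed from the Protocol. With equal visit rates across languages, the loss is bounded by the share of participants on those forms, and it is smaller to the extent that 8b or the Belgian linkage captures visits. No direction can be given for the between-arm cost difference. The primary and safety analyses are unaffected. This is a minor point, worth correcting because the correction is cheap.

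**What to change.** - Add the emergency department to question 8a in the English and French versions.
- Add an emergency-department row to question 8b in all three versions, Dutch included, so that these visits can be costed separately.
- Ask the nurse-practitioner line of question 1b in all three versions or in none.
- For forms already returned: leave the nurse-practitioner count out of the pooled cost, report that the English and French versions did not ask about emergency visits, and do not read their absence as zero use.

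The cost is a minor amendment to the wording of the questionnaires and one data-handling rule. No extra patients or procedures are needed.

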**Vraag 8b. Bij welke soorten dokters bent u in de afgelopen 3 maanden in het ziekenhuis geweest? En hoe vaak?**

Bij welke soort dokter bent u in het ziekenhuis geweest?	Hoe vaak bent u in de afgelopen 3 maanden bij deze dokter geweest?
voorbeeld cardioloog	voorbeeld 2 keer
.....	... keer
.....	... keer
.....	... keer
.....	... keer
.....	... keer
.....	... keer
.....	... keer
.....	... keer

**Vraag 9a. Heeft u in de afgelopen 3 maanden opnieuw in het ziekenhuis gelegen?**

U moest dus blijven slapen.

- Nee
- Ja

Heeft u “Ja” aangekruist? Beantwoord dan vraag 9b.

Ga anders verder met vraag 10.

**Vraag 9b. Hoe lang heeft u in het ziekenhuis gelegen?** Heeft u meer dan 1 keer in het ziekenhuis gelegen in de afgelopen 3 maanden? Tel dan alle dagen bij elkaar op.  
..... dagen in totaal in de afgelopen 3 maanden

**Vraag 10a. Bent u in de afgelopen 3 maanden ergens anders geweest dan in het ziekenhuis voor een behandeling?** Bijvoorbeeld naar een woon-/zorgcentrum of een psychiatrische instelling. Of naar een revalidatiecentrum.

- Nee
- Ja, maar ik ging daar alleen overdag naartoe
- Ja, ik was daar opgenomen (ik bleef daar slapen)

Heeft u “Ja” aangekruist? Beantwoord dan vraag 10b en 10c.

Anders was dit de laatste vraag.

**Vraag 10b. Wat voor instelling was dit?** Kruis het goede antwoord aan. U kunt meer dan 1 hokje aankruisen.

- Woon-/zorgcentrum
- Revalidatiecentrum
- Psychiatrische instelling
- Een andere instelling, namelijk .....

**Vraag 10c. Hoe lang bent u in deze instelling geweest?** Heeft u bij vraag 11b meer dan 1 hokje aangekruist? Vul dan hieronder voor iedere instelling in hoe lang u er bent geweest. Bent u ergens meer dan 1 keer geweest in de afgelopen 3 maanden? Tel dan alle dagen en nachten bij elkaar op.

In het woon-/zorgcentrum: ..... dagen en ..... nachten in de afgelopen 3 maanden

In het revalidatiecentrum: ..... dagen en ..... nachten in de afgelopen 3 maanden

In de psychiatrische instelling: ..... dagen en ..... nachten in de afgelopen 3 maanden

In de andere instelling: ..... dagen en ..... nachten in de afgelopen 3 maanden

Dit was de laatste vraag.

**Heeft u vragen of opmerkingen?**

Misschien heeft u nog vragen of opmerkingen? Schrijft u deze dan hieronder op.

.....  
.....

**Hartelijk dank!**

**17.8 Institute for Medical Technology Assessment Medical Consumption  
Questionnaire Vragenlijst Productivity & Health Research Group (iMTA MCQ) –  
English (Version 3.0, 13/07/2023)**

Researchers call this questionnaire the iMTA MCQ (iMCQ).

## **Comment**

### **Please read this first!**

#### **Can you not fill in the list yourself?**

If you cannot fill in the list yourself, someone might be able to help you. For example, a family member.

#### **What is the questionnaire about?**

The questionnaire is about your use of care in the past 3 months.

#### **How long does it take to fill in the list?**

It takes about 20 minutes to fill in the list.

#### **How do you have to fill in the list?**

- Start with the first question and follow the numbering.
- For each question, tick 1 box, except if the question states that you can tick more than 1 box.
- For some questions you can enter a number or something else on the dotted line.
- You cannot give wrong answers.

#### **What happens to your answers?**

Your answers are used for research. Only the researchers will see your answers. So no one else.

The researchers will not write down your name anywhere. And they will not tell anyone that you have taken part in the trial.

### **Thank you for filling in the list for us!**

## Questions about healthcare use

### Comment

We would like to know which doctors you have consulted in the past 3 months. It is about consultations for yourself. Other healthcare providers also count. For example, the physiotherapist.

Which consultations count?

Control visits

- 
- Appointments because you had a physical or psychological complaint
- Appointments where the doctor came to your home
- Telephone appointments
- Phone calls with the recipe line

Which consultations do not count?

- Appointments for another person, for example for your child
- Telephone calls to make an appointment

Are you unsure about the exact number of consultations? Please fill in how many consultations you have had approximately.

### Question 1a. Have you consulted a general practitioner in the past 3 months?

- No  
 Yes

Have you ticked "Yes"? Then answer question 1b.  
Otherwise, continue with question 2.

### Question 1b. How many appointments did you have with your general practitioner in the past 3 months?

- ..... appointments with a doctor  
 ..... appointments with a nurse practitioner

**Question 2. How many appointments did you have with a physiotherapist in the past 3 months? Or with a Caesar therapist, therapist Mensendieck or a manual therapist?** Add up all appointments with these therapists.

- No appointment
- ..... appointments

**Question 3. How many appointments did you have with an occupational therapist in the past 3 months?**

- No appointment
- ..... appointments

**Question 4. How many appointments did you have with a speech therapist in the past 3 months?**

- No appointment
- ..... appointments

**Question 5. How many appointments did you have with a psychologist in the past 3 months? Or with a psychotherapist or psychiatrist?** Add up all appointments with these healthcare providers.

- No appointment
- ..... appointments

**Question 6a. Have you received home care in the past 3 months?**

- No
- Yes

Have you ticked "Yes"? Then answer questions 6b through 6d. Otherwise, continue with question 7.

**Question 6b. What kind home care have you had in the past 3 months?** You can tick more than 1 box.

- Housekeeping and domestic help  
*example: vacuuming, making the bed, going for daily groceries*
- Personal care  
*example: help with bathing or dressing*
- Nursing  
*example: putting on a bandage, administering medication, measuring blood pressure*

**Question 6c. How many weeks did you have this home care?** Count up all weeks in the past 3 months. *Note: a period of 3 months counts 13 weeks.*

Domestic help: ..... weeks in the past 3 months

Personal care: ..... weeks in the past 3 months

Nursing: ..... weeks in the past 3 months

**Question 6d. How many hours of home care did you receive on average in these weeks?**

Domestic help: on average ..... hours a week

Personal care: on average ..... hours a week

Nursing: on average ..... hours a week

**Question 7a. Did you take any blood thinners\* in the past 3 months?**

No

Yes

\* carbasalatecalcium (ascal, acetylsalicylic acid), clopidogrel (plavix, grepid, iscover), prasugrel (efient) , ticagrelor (brilique), dipyidamole (persantin), acenocoumarol (sintrom), fenprocoumon (marcoumar), dabigatran (pradaxa), rivaroxaban (xarelto), apixaban; (eliquis), edoxaban (lixiana)

Have you ticked "Yes"? Then fill in question 7b listing which medications you used and how much.

Otherwise, continue with question 8.

**Question 7b. What blood thinners did you take in the past 3 months?** By blood thinners we mean all drugs listed in Question 7a after the asterisk (\*). There are twoexamples below.

**Pay attention:** look at the package! It shows how much you had to take at each time. And how often you had to do so per day. ***Have you used more or less? Then enter how much you have actually used.***

What is the name of the medicine?	How much did you take at each time? Look at the packaging	How many times did you take this per day? Look at the packaging	On how many days in the past 3 months have you used the medication?
example 1 Carbasalate calcium	example 100 mg	example 1 time	example 14 days
example 2 clopidogrel	example 75 mg	example 1 time	example 90 days
.....	.....	.....	.....
.....	.....	.....	.....
.....	.....	.....	.....
.....	.....	.....	.....
.....	.....	.....	.....
.....	.....	.....	.....
.....	.....	.....	.....
.....	.....	.....	.....

**Question 8a. Did you have an appointment at the outpatient clinic of the hospital in the past 3 months?** It is about appointments for yourself with a doctor. For example with the cardiologist, rheumatologist or neurologist. Hospital admissions (i.e. with an overnight stay) do not count here, it is only regarding daytime visits.

- No
- Yes

Have you ticked "Yes"? Then fill in question 8b the types of doctors you have visited. And how often. There is an example in the first row. Otherwise, continue with question 9.

